9.4.3 Incomplete date for Previous/Concomitant medication

No date imputation will take place on previous/concomitant medication. However, medications with partial end dates will be considered to be previous medication.

Statistical analysis plan	Date:	27-Oct-2023	
Trial ID: SU-G-01	Version:	1.0	
EudraCT No.: 2020-000455-12	Status:	Final	
CONFIDENTIAL	Page:	38 of 47	

9.5 Further details pertaining to statistical analyses

Adjusted means for each treatment group, the absolute treatment difference with 95% CI and pvalue, and the relative treatment difference with 95% confidence interval will be presented. The 95% confidence interval for the relative difference will be calculated using Fieller's theorem (Fieller 1954) see **Error! Reference source not found.**

Fieller's method

In statistics, Fieller's theorem allows the calculation of a confidence interval for the ratio of two means. If the two means are normally distributed Fieller's formular is exact. The method calculates limits for $\frac{a}{b}$, \tilde{L} and \tilde{U} . Since the relative difference is $\hat{\rho}_{ii'} = \frac{(\hat{\mu}_i)^2 - (\hat{\mu}_{i'})^2}{(\hat{\mu}_{i'})^2} = 1 - \left(\frac{\hat{\mu}_{i'}}{\hat{\mu}_{i'}}\right)^2$, Fieller's limits are (back)transformed as $L = 1 - \tilde{L}^2$ and $U = 1 - \tilde{U}^2$ (or $U = 1 - \tilde{L}^2$ and $L = 1 - \tilde{U}^2$).

Importantly, Fieller's limits are calculated on the transformed-scale and via the above transformation the limites on the back-transformed scale is derived. Let

$$g = \left(\frac{t_{0.975,df} \cdot \operatorname{SE}(\hat{\tilde{\mu}}_{i'})}{\hat{\tilde{\mu}}_{i'}}\right)^2,$$

and

$$u = \mathrm{SE}^2(\hat{\tilde{\mu}}_i) - \frac{2\widehat{\mathrm{cov}}(\hat{\tilde{\mu}}_i, \hat{\tilde{\mu}}_{i'})\hat{\tilde{\mu}}_i}{\hat{\tilde{\mu}}_{i'}} + \left(\frac{\mathrm{SE}(\hat{\tilde{\mu}}_{i'})\hat{\tilde{\mu}}_i}{\hat{\tilde{\mu}}_{i'}}\right)^2 - g\left(\mathrm{SE}^2(\hat{\tilde{\mu}}_i) - \left(\frac{\widehat{\mathrm{cov}}(\hat{\tilde{\mu}}_i, \hat{\tilde{\mu}}_{i'})}{\mathrm{SE}(\hat{\tilde{\mu}}_{i'})}\right)^2\right),$$

then

$$L = 1 - \left(\frac{\frac{\hat{\mu}_i}{\hat{\mu}_{i'}} - g\frac{\widehat{\cos}(\hat{\mu}_i, \hat{\mu}_{i'})}{\mathrm{SE}^2(\hat{\mu}_{i'})} + \frac{t_{0.975, df}\sqrt{u}}{\hat{\mu}_{i'}}}{(1-g)}\right)^2$$

and

$$U = 1 - \left(\frac{\frac{\hat{\mu}_i}{\bar{\mu}_{i'}} - g\frac{\widehat{\text{cov}}(\hat{\mu}_i, \hat{\mu}_{i'})}{\text{SE}^2(\bar{\mu}_{i'})} - \frac{t_{0.975, df}\sqrt{u}}{\bar{\mu}_{i'}}}{(1-g)}\right)^2$$

Figure 3 Fieller's method

9.5.1 Transformations

Some endpoints will be square root transformed before (formal statistical) analysis. The square root transformation is generally applied, as this usually results in a good approximation to the normal distribution. In addition, a lot of subjects do not use rescue medication, so the average DMS score is often 0, and this will also be accounted for by using the square root transformation in contrast to the logarithmic transformation. The transformed endpoint is then included in the model as a response variable.

The p-value for the absolute difference will be reported as the test result and no backtransformation will be done. To enable reporting of relative difference on the original scale, transformed means will be back-transformed (see **Error! Reference source not found.**) and 95% CI will be calculated using the methods described in Figure 3. For the absolute difference,

Statistical analysis plan	Date:	27-Oct-2023		
Trial ID: SU-G-01	Version:	1.0	1	,
EudraCT No.: 2020-000455-12	Status:	Final		
CONFIDENTIAL	Page:	39 of 47		

the SE is approximated using the first-order Delta method (first-order Taylor approximation), and the 95% CI is calculated from this.

$\sqrt{()}$ -transformation

Means, differences between means and relative differences

For $\sqrt{()}$ -transformed endpoints the back-transformations (to the original scale) are :

$$\hat{\mu}_i = (\hat{\tilde{\mu}}_i)^2,$$

where $\hat{\mu}_i$ is the *i*'th treatment mean on the $\sqrt{()}$ -transformed scale. Similarly, back-transformed differences between group means are

$$\hat{\delta}_{ii'} = (\hat{\tilde{\mu}}_i)^2 - (\hat{\tilde{\mu}}_{i'})^2,$$

and relative differences are thus

$$\hat{\rho}_{ii'} = \frac{(\hat{\tilde{\mu}}_i)^2 - (\hat{\tilde{\mu}}_{i'})^2}{(\hat{\tilde{\mu}}_{i'})^2}.$$

The estimates $\hat{\mu}_i$, $\hat{\mu}_{i'}$ (that is, on the $\sqrt{()}$ -transformed scale) are obtained from proc mixed's lsmeans statement.

Standard errors

The variances of the back-transformed parameters follow from the δ -method

$$\operatorname{SE}(\hat{\mu}_i) = 2\hat{\tilde{\mu}}_i \times \operatorname{SE}(\hat{\tilde{\mu}}_i).$$

with the variance (SE) of $\hat{\delta}_{ii'}$ following alike :

$$\operatorname{SE}(\hat{\delta}_{ii'}) = 2\sqrt{\hat{\mu}_i^2}\operatorname{SE}^2(\hat{\mu}_i) + \hat{\mu}_{i'}^2\operatorname{SE}^2(\hat{\mu}_{i'}) - 2\hat{\mu}_i\hat{\mu}_{i'}\widehat{\operatorname{cov}}(\hat{\mu}_i, \hat{\mu}_{i'}).$$

The estimates $\hat{\tilde{\mu}}_i$, $\hat{\tilde{\mu}}_{i'}$, SE($\hat{\tilde{\mu}}_i$) and SE($\hat{\tilde{\mu}}_{i'}$) (that is, on the $\sqrt{()}$ -transformed scale) are obtained from proc mixed's lsmeans statement.

Figure 4 Transformations

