7	Supportive secondary endpoint: DMS 1st PGPS	Supportive secondary endpoint: DMS 2nd PGPS
8	Supportive secondary endpoint: DMS 1st EGPS	Supportive secondary endpoint: DMS 2nd EGPS

Table 11Summary of MMRM response variables.

The relevant endpoints in 1st and 2nd years are set to be the response variables and treatment, visit, treatment/visit interaction as well as asthma indication (yes/no) are fixed effect and trial site as a random class effect. If less than 20% of subjects will have asthma indication positive, then the asthma indication will be removed from the model. The compound symmetry covariance matrix is considered. In case there will be issues with convergence, first-order autoregressive covariance matrix will be considered. Depending on the number and size of trial sites, pooling of trial sites may be considered, or trial sites may be replaced by regions or countries. This will be specified in the SAP. The summary of the results will contain p-value for the treatment effect, and both the absolute difference with 95% CI and the relative difference with 95% CI will be presented. If the assumptions underlying the MMRM are not fulfilled an appropriate transformation (e.g. the square root) of the response variables will be carried out. Results will be back-transformed and shown on

Clinical trial protocol Trial ID: SU-G-01 EudraCT No. 2020-000455-12 CONFIDENTIAI	Date: Version: Status: Page:	12-Nov-2021 4.0 Final 63 of 77	
CONFIDENTIAL	гауе.	03 01 7 7	

the original scale. Further details of the primary analysis, test of assumptions, and sensitivity analysis will be detailed in the SAP.

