3.1.1.2 Primary estimand

Primary estimand is referred to as the 'trial product estimand'. The trial product estimand assesses the anticipated effect of the 5-grass SLIT-drops if it is taken as instructed. This estimand is considered to be of most relevance to the patient population, as it describes the potential benefit they could obtain from the 5-grass SLIT-drops if they adhere to treatment for the planned duration. Adherence to treatment is considered important in immunotherapy since the optimal effect of immunotherapy is expected when taken consistently for a longer period.

Using the framework proposed in the ICH 2020, the trial product estimand can be described by:

- A. **Treatment:** 5-grass mix SLIT-drops, where rescue medication is taken as required
- B. **Population**: adults with grass pollen-induced rhinoconjunctivitis
- C. **Variables**: average daily allergic rhinoconjunctivitis TCS during 2nd PGPS
- D. **How to account for intercurrent events:** under the hypothetical situation where all subjects have completed treatment for the planned duration (hypothetical strategy).
- E. **Population summary**: absolute difference in means between treatment (see Section 9.5).

Statistical analysis plan	Date:	27-Oct-2023	A Lk
Trial ID: SU-G-01	Version:	1.0	
EudraCT No.: 2020-000455-12	Status:	Final	
CONFIDENTIAL	Page:	13 of 47	
	Page.	13 01 47	

A hypothetical strategy is used to address the intercurrent event of discontinuation of trial treatment. As such, if a subject discontinues trial treatment, only diary data up until the time of discontinuation is included in the analysis. Any diary data recorded after the discontinuation of trial treatment will be excluded from the analysis. Details of the handling of IEs for primary estimand main estimator are provided in section 6.2.1.

Put differently, the hypothetical assumption is that subjects remain on randomised treatment, but this does not necessarily imply that all subjects randomised to the same treatment experience similar benefits of that treatment. The determining factor is discontinuation of IMP due to following reasons (see section 6.1.2):

- due to "lack of efficacy"
- due to "IMP-related AEs"
- due to "other reasons"

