4.1 Multiplicity adjustment

The trial product estimand is the primary estimand for all endpoints. The analyses for the primary and for the three key secondary endpoints will be controlled for multiplicity to ensure a family wise type I error rate is no larger than 5%.

The multiplicity will be controlled by employing a hierarchical testing procedure by prespecifying the order of the hypothesis to be tested. For the primary and key secondary endpoints the null hypothesis tested, is the hypothesis no difference between placebo and 5grass mix SLIT-drops treatment group.

The testing order of hypothesis is:

- 1. The primary efficacy analysis of the average daily allergic rhinoconjunctivitis TCS during the 2nd PGPS.
- 2. The key secondary efficacy analysis of average weekly overall RQLQ score during the 2nd PGPS.

Statistical analysis plan	Date:	27-Oct-2023	
Trial ID: SU-G-01	Version:	1.0	
EudraCT No.: 2020-000455-12	Status:	Final	
CONFIDENTIAL	Page:	16 of 47	

- 3. The key secondary efficacy analysis of average daily allergic rhinoconjunctivitis TCS during the 1st PGPS.
- 4. The key secondary efficacy analysis of average weekly overall RQLQ score during the 1st PGPS.

The primary endpoint is the 1st hypothesis in the hierarchy and will be tested on a 5% significance level. The testing of endpoints from the 2nd to the 4th in the hypothesis hierarchy will only be is only carried out formally if all previously tested hypotheses are statistically significant at the 5% level.

Additional endpoints and analyses are supportive in nature, thus they will not be controlled for multiplicity.

5 Analysis sets

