6.1 General considerations

The efficacy data will be analyzed using estimand framework. The primary and first key secondary endpoints will be analyzed based on on-treatment (DPS1) and in-trial (DPS2) data, while the rest of the endpoints will be analyzed based on on-treatment (DPS1) data. Different approaches of handling missing data will be applied. Overview of analysis methods and analysis sets to be used are summarized in **Error! Reference source not found.**

Table 4 Summary of analyses

Enapoint	Analysis methods	Analysis sets	Data type
	Trial product estimand – main approach		Imputed, DPS1
	Trial product estimand – sensitivity analysis		
	Treatment policy estimand – main approach		Imputed DBS2
	Treatment policy estimand – sensitivity analysis		
Primary endpoint:TCS during 2 nd PGPS	Supportive analysis: Tipping- point analysis under the trial estimand – main approach	FAS	
Key secondary enpoind: RQLQ during 2 nd PGPS	Supplementary analysis: Ongoing asthma subgroup analysis		Imputed, DPS1
	Supplementary analysis: Subjects from the same household		
	Supplementary analysis: Symptoms-score tertiles analysis		Observed, DPS1
	Descriptive analysis	FAS/AAS	
	Trial product estimand – main approach		Imputed DPS1
Key secondary enpoind:	Trial product estimand – sensitivity analysis		
TCS during 1 st EGPS RQLQ during 1 st EGPS	Treatment policy estimand – main approach	FAS	Imputed DPS1
	Treatment policy estimand – sensitivity analysis		
	Descriptive analysis		Observed, DPS1
Secondary endpoints:	Trial product estimand – main approach	FAS	Imputed, DPS1
	Descriptive analysis		Observed, DPS1
Secondary endpoints:	Descriptive analysis	SAF	Observed

Unless otherwise mentioned all the statistical tests described in this section will use a significance level of 5% and all tests and confidence intervals will be two-sided. All null hypotheses are "*no differences in means between treatment arms*" and the alternative hypotheses will always be "*a (not specified) difference*".

Descriptive statistics for efficacy endpoints will be based on observed on-treatment data. Descriptive statistics for numerical (continuous) variables include displaying treatment group mean, SD, median, minimum and maximum. Descriptive statistics for categorical variables will include frequency tables displaying the numbers and percentages.

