9.5.2 Analyses with multiple imputation

The imputations will be carried out using the method of unrestricted random sampling with replacement (seed = 68686) and with 1,000 multiple imputed datasets created. It means that observed data is "bootstrapped" or sampled with replacement within the strata defined in the rows of Table 5, Table 6 and Table 7 and used to substitute (impute) missing data. If the actual significance level of the performed test will be between 4%-6%, then the number of imputations will be increased from 1,000 to 10,000. This will be done to ensure the precision of estimated standard error, and thus the right hypothesis testing conclusion will be made.

Statistical analysis plan Trial ID: SU-G-01	Date: Version:	27-Oct-2023 1.0		
EudraCT No.: 2020-000455-12	Status:	Final		
CONFIDENTIAL	Page:	40 of 47		

Missing data for each year will be imputed based on observed cases for the same year and using subjects as source for the imputations which happen to have data in the "current" year in question.

Further, PGPS data will be imputed from observed PGPS data and EGPS from EGPS data from the corresponding year and ongoing asthma status. The ongoing asthma status might only be considered if there is enough unique permutation to impute from.

The relevant endpoints in 1st and 2nd years will be analysed using a MMRM with treatment and year interaction, and ongoing asthma status as fixed effects and country and year interaction as random class effect and allowing unequal R-matrices among the two treatment arms. After the by-imputation MMRMs, results are summaries/combined using Rubin's method (**Rubin 1987**).

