9.5.3 Model checking

The assumption of normally distributed residuals will be evaluated by visual inspection of quantile-quantile plots for the primary and key secondary endpoints. If the square root transformation does not result in a good approximation to the normal distribution, no transformation will be applied if this improves the approximation to a normal distribution.

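### Squaring square-root LS means does not give the difference in means the estimand names, and the relative difference and its confidence limits are defined with opposite signs

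*SAP*

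**What the plan says.** **Estimand.** Protocol 15.1.2 and 15.1.3 give the population summary as an absolute difference in means. SAP 3.1.1.2 says "absolute difference in means between treatment (see Section 9.5", and 3.1.1.3 says the same for the secondary estimand.

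**Null hypothesis.** SAP 6.1 words it as "no differences in means between treatment arms". SAP 4.1 is more general: "the null hypothesis tested, is the hypothesis no difference between placebo and" the active group.

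**Transformation.** SAP 9.5.1 says that some endpoints will be transformed, without listing them, and adds "The square root transformation is generally applied, as this usually results in a good approximation to the normal distribution". SAP 9.5.3, on the primary and key secondary endpoints, makes the untransformed scale the fallback: "If the square root transformation does not result in a good approximation to the normal distribution, no transformation will be applied" if that improves the fit. The protocol (15.11.1) had it the other way round: "If the assumptions underlying the MMRM are not fulfilled an appropriate transformation (e.g. the square root") would be used. SAP 6.5 lists changes from the protocol but not this one.

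**Back-transformation.** In Figure 4 an arm's mean is its squared square-root LS mean, the absolute difference is the difference of those squares, and the relative difference is that difference divided by the reference arm's square. No variance term is added. The model in 9.5.2 is fitted "allowing unequal R-matrices among the two treatment arms".

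**Relative interval.** In Figure 3, "Fieller's limits are (back)transformed as" one minus the squared limit, for both limits.

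**The concern.** The square of a mean square root is not a mean. The gap is the variance on the square-root scale, and it drops out of a between-arm difference only if that variance is the same in both arms. The plan does not assume that. The primary TCS result could therefore be labelled a difference in means on the original scale while estimating something else, with an error whose size and direction are not known beforehand. Arm means and relative reductions are affected even when the variances are equal.

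The sign conflict is a separate defect. An estimate and its interval with opposite signs cannot both be printed, and a final SAP should not leave the programmer to choose between them.

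The p-values come from the transformed model and are not back-transformed, so type I error and the hierarchy are not at stake. The size of effect is, in a trial meant to support reimbursement (protocol 1.3).

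**Working it through.** **Reproducing the plan's own figure.** SAP 7 uses a TCS difference of 1.64, common SD 5.5 and 180 evaluable per arm. SE = 5.5 × √(2/180) = 0.580; 1.64/0.580 = 2.83; power = Φ(2.83 − 1.96) ≈ 81%, against the stated 80%. The planning is therefore on untransformed means.

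**The identity.** For arm means m and variances v on the square-root scale,

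E[Y] = m² + v, so the true difference = (m_P² − m_A²) + (v_P − v_A).

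Figure 4 keeps only the first bracket.

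**Inputs and assumed shapes.** The documents give no square-root-scale moments, so I matched the means (E) and SDs (S) of SAP Table 8 and protocol Table 9 under two assumed shapes:

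- Normal on the square-root scale: solving m² + v = E and 4m²v + 2v² = S² gives m² = √(E² − S²/2).
- Gamma on the original scale: k = (E/S)², θ = S²/E, m = √θ · Γ(k + ½)/Γ(k), v = E − m².

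**Worked row, P05238 TCS, square-root normal.**

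- Placebo: m² = √(7.74² − 6.50²/2) = 6.23, v = 1.51.
- Active: m² = √(6.10² − 5.09²/2) = 4.93, v = 1.18 (unrounded 1.175).
- Reported difference 1.30; omitted variance difference 0.34; sum 1.64.

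**Results** (placebo minus active; square-root normal / gamma):

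| Moments | True difference | Reported | Reported ÷ true | True relative | Reported relative |
|---|---|---|---|---|---|
| TCS GT-08 2006 | 3.30 | 3.23 / 3.19 | 98% / 97% | 39% | 43% / 42% |
| TCS P05238 | 1.64 | 1.30 / 1.37 | 79% / 83% | 21.2% | 20.9% / 21.0% |
| TCS P08067 | 1.17 | 1.30 / 1.18 | 111% / 101% | 20% | 29% / 25% |
| TCS planning (P05238 means, SD 5.5) | 1.64 | 1.99 / 1.83 | 121% / 112% | 21% | 30% / 27% |

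The same calculation for RQLQ (true differences are the row means subtracted):

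| Moments | True difference | Reported |
|---|---|---|
| GT-08 2005 | 0.45 | 0.456 / 0.449 |
| GT-08 2006 | 0.43 | 0.451 / 0.433 |
| P05238 | 0.32 | 0.281 / 0.285 |
| P08067 (protocol row) | 0.14 | 0.162 / 0.148 |
| Planning (1.60 v 1.26, SD 1.15) | 0.34 | 0.415 / 0.380 |

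SAP Table 9 prints a different P08067 placebo entry, 1.73 (1.34). With it, a true 0.55 is reported as 0.548 / 0.530. No RQLQ value crosses the SAP's MCID of 0.10.

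**Sign.** Let r be the ratio of square-root LS means, active over placebo. Figure 4 gives r² − 1. Figure 3's L and U are 1 − (Fieller limit for r)². The interval contains 1 − r², the negative of the estimate, so whenever it excludes zero it must miss its own estimate.

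Example: P05238, square-root normal, 180 per arm, 358 df, covariance taken as zero.

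- r = 2.496/2.219 inverted, i.e. 2.219/2.496 = 0.889, so the estimate is r² − 1 = −20.9%.
- The Fieller limits for r are 0.803 and 0.985, so L = 1 − 0.985² = +3.0% and U = 1 − 0.803² = +35.5%.
- P08067 gives −28.9% with +9.3% to +44.6%.
- Taking placebo as arm i does not help: P05238 becomes +26.4% with −55.0% to −3.1%.

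**The case against.** **The protocol foresaw this.** Protocol 15.11.1 names the square root as its example, says results will be back-transformed to the original scale, and leaves details to the SAP. The SAP estimand points to Section 9.5, where the formulas are set out openly. This shows that the method is disclosed. It does not make the result a difference in means, which is still what the SAP text says, and the protocol estimand carries no such pointer.

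**The error is modest and depends on assumptions.** At 180 per arm the raw-scale 95% half-width is about 1.0 to 1.2 TCS points; for P05238 it is 1.967 × √((6.50² + 5.09²)/180) = 1.21. The error there is 0.27 to 0.34. The largest overstatement comes from the planning case, which combines P05238 means with a common SD, whereas every source row has a smaller SD on active. The square-root normal shape also puts about 6% of P08067's active arm below zero, which cannot occur; gamma gives 101% there. The SAP's P08067 RQLQ row conflicts with its own printed difference of 0.15 and looks like a copying error. All of this is fair and limits the size claimed. The identity itself needs no shape assumption.

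**The sign point is a slip that would be noticed.** Probably so. Figure 3 evidently intends a reduction, and the primary SAS code is not in the copy reviewed, so what was programmed is unknown. The middle ratio in Figure 3 is also damaged in the text; the conflict rests on the legible L and U formulas and on Figure 4.

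**The wording of the null matters little.** A test of equal square-root means is valid for the no-difference null in 4.1. It differs only from the means wording in 6.1.

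**Conclusion.** The point holds. As written, the absolute difference in 9.5.1 equals the estimand's difference in means only if the square-root-scale variance is equal in the two arms. The arm means and relative difference are off even then: P05238 placebo would be shown as 6.2 to 6.5 instead of 7.74. Across the three TCS source trials the reported absolute difference is 79% to 111% of the true one, and in the planning case 112% to 121%. The direction is not predictable, and in one row (the P05238 relative difference) there is almost no error. These sizes rest on the two assumed shapes and on marginal SDs.

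The opposite signs of the relative difference and its interval follow from algebra alone. The unlisted move from conditional to default transformation is a documentation gap. No test or hierarchy decision changes, but the effect sizes should be corrected before they are reported.

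**What to change.** - **Absolute difference.** Report the estimand's difference and 95% CI from the same MMRM fitted to the untransformed score on the same imputed datasets. Alternatively, add each arm's and year's model variance on the square-root scale to its squared LS mean before differencing, with a matching SE. That alternative is for the absolute difference only: LS means also average over asthma status, and the resulting spread cancels between arms but is still missing from the single means and the relative difference.
- **p-value.** The square-root p-value can stay, with its null stated as equality of square-root-scale means.
- **Sign.** Most simply, define the relative difference as a reduction, 1 − (active/placebo)² on the square-root LS means. This matches the positive percentages in Tables 8 and 9 and keeps Figure 3's limits. Otherwise use (Fieller limit)² − 1 for both limits.
- **Documentation.** Name the endpoints to be transformed, and list the change from conditional to default transformation in SAP 6.5.

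The cost is SAP wording and one extra model run per endpoint. One small downside is that the raw-scale interval and the square-root p-value may disagree near the 5% boundary, so the SAP should say in advance that the p-value decides the test.
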